### Combination CB-839 and 5-fluorouracil shrinks PIK3CA mutant xenograft tumors

Based on tissue culture data demonstrating that 5-fluorouracil enhanced cytotoxicity of CB-839, our group sought to determine if CB-839 alone or in combination with 5-fluorouracil inhibits xenograft tumor growth of a PIK3CA mutant colorectal cancer. A dose of 30mg/kg of 5-fluorouracil was tested after it was determined that 40mg/kg was the maximum tolerated dose in mice. Mice were treated with 200mg/kg CB-839 and 30mg/kg 5-fluorouracil combination therapy which induced tumor regression (Fig 2). In contrast, although CB-839 and 5-fluorouracil alone each inhibited tumor growth to various extents, neither induced tumor regression. Furthermore, combination of CB-839 and 5-fluorouracil also induced tumor regression of a patient derived xenograft. Overall, these results provide a strong rationale for conduct of a clinical trial assessing the combination of CB-839 and 5-fluorouracil in colorectal cancer with PIK3CA mutations.

### Combination of CB-839 and 5-fluorouracil depletes cellular dTTP levels

Given that glutamine is a precursor for nucleotide synthesis and that 5-FU is a thymidylate synthase inhibitor, we set to determine how the drug combination impacts cellular dTTP levels. As shown in Fig. 3, either drug alone significantly reduced amounts of dTTP, whereas the combination of CB-839 and 5-FU nearly completely depleted cellular dTTP. These data suggest that CB-839 enhances the cytotoxicity of 5-FU by further depleting cellular dTTP.

**Fig. 3. Combination CB-839 and 5-FU depletes cellular dTTP levels.** HCT116 cells were treated with the indicated drugs. Cellular dTTP amounts were measured by LC-MS/MS.

#### 1.2.2 Clinical Data

A phase I study assessed CB-839 administered as a single agent in patients with metastatic solid tumors (17, 18), cumulative exposure to date is 125 patients (data cut 26 January 2016). Patients received CB-839 according to either a three times daily (TID) dosing schedule or a twice daily

dosing schedule (BID with food) during a 21-day treatment cycle. A standard 3+3 dose escalation strategy was employed assessing dose levels ranging from 100-800 mg TID (n=32), and 600-800 mg BID with food (n=27). Treatment was well tolerated with 16% of patients across all trials experiencing a grade 3/4 treatment related adverse event. One dose limiting toxicity occurred (grade 3 creatinine in a patient with known diabetes). The majority of adverse events were related to asymptomatic, reversible elevations in liver function tests (LFTs). Twice daily dosing with food resulted in a lower frequency (1.5%) of grade 3 treatment-related LFT abnormalities than TID dosing and hence has been selected as the dosing schedule to pursue in subsequent studies (18). Pharmacodynamic analyses (see section 1.2.3) have demonstrated that 600 mg BID results in continuous strong glutaminase inhibition in most patients and is a sufficient dose for further study. Expansion cohorts assessing single agent activity of CB-839 600 mg BID have been enrolled in triple negative breast cancer, KRAS-mutant non-small cell lung cancer, renal cell carcinoma, mesothelioma, fumarate-hydratase (FH)-deficient solid tumors, succinate dehydrogenase (SDH)-deficient GIST, succinate dehydrogenase (SDH)-deficient non-GIST and isocitrate dehydrogenase (IDH)-mutant solid tumors and have confirmed the adverse event profile and recommended phase 2 dose (18). Monotherapy dosing at 800 mg BID has also been shown to be safe and well tolerated and is being further explored in the clinic—this dose could eventually become the preferred recommended phase 2 dose. Two-drug combination studies with CB-839 and either paclitaxel, erlotinib, everolimus or docetaxel are planned.

Two phase I studies of CB-839 administered as a single agent were also conducted in patients with hematologic malignancies: relapsed and/or treatment refractory multiple myeloma or non-Hodgkins lymphoma (CX-839-02) and relapsed and/or treatment refractory leukemia and IDH-mutated myelodysplastic syndrome (CX-839-003) were also conducted (19). Totals of 14 and 18 patients received CB-839 in CX-839-002 and CX-839-003, respectively according to the same treatment strategy employed in the aforementioned solid tumor study. Treatment was similarly tolerated with 21% and 14% of patients respectively experiencing a grade 3/4 adverse event thought to be related to CB-839. The majority of the adverse events were due to asymptomatic, reversible LFT abnormalities or hematological adverse events. Given the larger experience in the solid tumor phase I study, BID dosing was selected for subsequent studies hematologic malignancy studies. Expansion cohorts assessing single agent activity of CB-639 600 mg BID are ongoing in acute myeloid leukemia (IDH wild-type), acute lymphoid leukemia, acute myeloid leukemia (IDH1 or IDH2 mutant) and myelodysplastic syndrome (IDH1 or IDH2 mutant).

### 1.2.3 Clinical Pharmacokinetics and Pharmacodynamics

Pharmacokinetic sampling was performed on Cycle 1, Day 1 (C1D1), C1D15 and D1 of each subsequent treatment cycle in each of the conducted phase I studies (17-19). A dose dependent relationship was observed with CB-839 exposure increasing with dose. The half-life of CB-839 was determined to be 4 hours. Additionally, Cmin fell below a target concentration of 200 ng/mL in 46% of patients receiving 400 mg or higher TID regimens while a large majority of patients receiving BID dosing with 600 mg maintained a Cmin greater than the 200 ng/mL target concentration. Additionally, an assessment of the effect of food on the PK profile of CB-839 demonstrated a modest positive food effect and delayed absorption, which resulted in similar Cmax and Cmin for the 600 mg TID and 600 mg BID fed regimens. Given the favorable adverse event profile observed with the 600 mg BID fed regimen, this is the favored dosing regimen.

Pharmacodynamics of CB-839 was also assessed in both studies. Glutaminase activity was measured in circulating platelets as well as tumor biopsy specimens. Blood samples collected at baseline and four hours following CB-839 treatment were assessed for glutaminase inhibition and demonstrated a dose dependent relationship. At a CB-839 treatment dose of 600 mg BID, greater than 90% glutaminase inhibition should be observed even at Cmin for most patients. An evaluation of glutaminase activity assessed approximately 4 hours after the C1D15 CB-839 dose within five (5) tumor specimens also demonstrated clear inhibition of glutaminase activity and suggested a dose-response relationship (18).

Based on both pharmacokinetics and pharmacodynamics, CB-839 600 mg BID or 800 mg BID for a 21-day treatment cycle, to be repeated every 21 days has been determined as the single agent dose for pursuit in further clinical trials.

### **1.3 Capecitabine**

#### **1.3.1 Clinical Data**

Capecitabine is an oral fluoropyrimidine and is a prodrug of 5-fluorouracil. Per the National Comprehensive Cancer Network guidelines (2), capecitabine and 5-FU are considered equivalent and either may be used as frontline treatment for colorectal cancer, typically in combination with another chemotherapeutic agent (oxaliplatin or irinotecan) and a biologic agent (either an EGFR inhibitor or a VEGF inhibitor). It may also be used as a single agent as a maintenance therapy. Ultimately patients develop resistance to fluoropyrimidine therapy and hence disease progression. However, based on our preclinical data outlined in section 1.2.1, we hypothesize that co-administration of CB-839 with capecitabine will overcome fluoropyrimidine resistance, particularly in PIK3CA mutant colorectal cancers, and therefore capecitabine will be used as the cytotoxic backbone for this study.

### **1.4 Rationale for clinical and correlative studies**

It has been demonstrated that CB-839, via targeting glutaminase, inhibits xenograft growth in 2 of 2 PIK3CA mutant colon cancer test xenograft models but does not inhibit growth in PIK3CA WT models, supporting that there is an addiction of PIK3CA mutant colorectal cancers to glutamine metabolism. Furthermore, CB-839 plus 5-FU shrinks 2 of 2 PIK3CA mutant xenografts that both grow through maximally tolerated doses of 5-FU alone. Based on these findings, we propose to test responses of the CB-839 and fluoropyrimidine combination in fluoropyrimidine resistant human patients. Based on our preclinical mechanistic studies described above, we propose a phase I clinical trial to determine the maximum tolerated dose (MTD), recommended phase 2 dose (RP2D) and dose limiting toxicities of CB-839 plus capecitabine in patients with advanced solid tumors. The data derived from this trial will be used for a subsequent phase II clinical trial where we will estimate the antitumor activity and pharmacodynamic effects of CB-839 and capecitabine in patients with PIK3CA mutant colorectal cancers that are resistant to fluoropyrimidine therapy. We hypothesize that CB-839 in combination with capecitabine will overcome fluoropyrimidine resistance and that the addition of capecitabine to CB-839 will result in the inhibition of glutaminase in tumors and platelets and the reduction in nucleotide levels in tumors. Genomic abnormalities on the DNA and RNA level will also be explored via a whole exome sequencing

analysis and an RNA seq analysis.

As of January 2018, the phase I portion of the study has been fully accrued. A total of 16 patients were treated on the study and we were able to assess all of the four planned dose levels. No dose limiting toxicities were observed and we have therefore determined that the recommended phase II dose be CB-839 800 mg by mouth twice daily continuously and capecitabine 1000 mg/m^2 orally twice daily on days 1-14 of a 21 day treatment cycle.

## **2.0 OBJECTIVES**

The overall objectives for this study are to 1) determine the recommended phase II dose (RP2D) of CB-839 and capecitabine in patients with advanced solid tumors who have no further treatment options or patients for whom single agent capecitabine is an acceptable treatment regimen and 2) to determine the antitumor activity of CB-839 and capecitabine chemotherapy in patients with metastatic PIK3CA mutant colorectal cancer who are refractory to fluoropyrimidine based therapy. The phase I portion of this study will also determine the dose-limiting toxicities of this treatment regimen as well as the pharmacokinetics. In the phase II portion of this study, the pharmacodynamic effects of CB-839 and capecitabine will be evaluated using multiple biomarker studies including glutaminase activity level and nucleotide levels as well as a whole exome sequencing analysis and an RNA seq analysis. We hypothesize that we will observe a reduction in glutaminase activity in both tumors and platelets and a reduction in nucleotide levels following treatment. The whole exome and RNA seq analyses will be exploratory. The generation of organoids from tumor biopsy specimens both prior to and following treatment will also be exploratory and will be used for further potential studies as additional preclinical information becomes available

### **2.1 Primary Objective**

- 2.1.1 Phase I: To determine the safety, tolerability and recommended phase II dose (RP2D) of combination CB-839 and capecitabine chemotherapy in patients with advanced solid tumors for whom there are no remaining treatment options or for whom single agent capecitabine is an acceptable therapy.
- 2.1.2 Phase II: To determine the disease control rate of combination CB-839 and capecitabine chemotherapy in patients with metastatic PIK3CA mutant colorectal cancers who are refractory to fluoropyrimidine based therapy.

### **2.2 Secondary Objectives**

#### **2.2.1 Phase I**

To determine the dose-limiting toxicities and maximum tolerated dose of combination therapy with CB-839 and capecitabine in patients with advanced solid tumors for whom there are no remaining treatment options or for whom single agent capecitabine is an acceptable therapy.

To determine the antitumor response as assessed by RECIST criteria of combination therapy with CB-839 and capecitabine in patients with advanced solid tumors for whom there are no remaining treatment options or for whom single agent capecitabine is an acceptable therapy.

#### 2.2.2 Phase II

To determine the progression free survival following treatment with CB-839 and capecitabine chemotherapy in patients with metastatic PIK3CA mutant colorectal cancer and are refractory to fluoropyrimidine based therapy.

To determine the overall survival following treatment with CB-839 and capecitabine chemotherapy in patients who have metastatic PIK3CA mutant colorectal cancer and are refractory to fluoropyrimidine based therapy.

### 2.3 **Correlative Objective(s)**

#### 2.3.1 Phase II

To determine the change in glutaminase activity level in tumor specimens and platelets following treatment with CB-839 and capecitabine chemotherapy in patients with metastatic PIK3CA mutant colorectal cancer who are refractory to fluoropyrimidine based therapy.

To determine the reduction in nucleotide levels in tumor specimens following treatment with CB-839 and capecitabine chemotherapy in patients with metastatic PIK3CA mutant colorectal cancer who are refractory to fluoropyrimidine based therapy.

To determine genomic changes in both DNA and RNA in tumor specimens following treatment with CB-839 and capecitabine chemotherapy in patients with metastatic PIK3CA mutant colorectal cancer who are refractory to fluoropyrimidine based therapy.

To determine the correlation between plasma trough levels of CB-839 and biomarkers of interest in patients with metastatic PIK3CA mutant colorectal cancer who are refractory to fluoropyrimidine based therapy and who have received treatment with CB-839 and capecitabine chemotherapy.

To determine the correlation between clinical response to treatment and biomarkers of interest in patients with metastatic PIK3CA mutant colorectal cancer who are refractory to fluoropyrimidine based therapy and who have received treatment with CB-839 and capecitabine chemotherapy.

To generate organoids from patient tissue biopsies obtained prior to and following treatment in patients treated with CB-839 and capecitabine chemotherapy in patients with metastatic PIK3CA mutant colorectal cancer who are refractory of fluoropyrimidine based therapy.

## 3.0 STUDY DESIGN

### 3.1 Study design including dose escalation / cohorts for phase I component

This is a standard 3+3 phase I dose escalation trial to determine the maximum tolerated dose and dose limiting toxicities of combination therapy with CB-839 and capecitabine chemotherapy in patients with advanced solid tumors with no remaining treatment options or for whom single agent capecitabine is an acceptable therapy. Patients will receive combination therapy with CB-839 and capecitabine for 21 day cycles and will remain on treatment until either disease progression, development of unacceptable toxicity or discontinuation per patient/physician preference. Patients will receive CB-839 orally twice daily for 21 days (continuous administration) and capecitabine orally twice daily for 14/21 days. Dosing of CB-839 and capecitabine will occur according to the following dosing table. Day 15 trough CB-839 levels will be obtained for pharmacokinetic assessment. Patients will undergo a CT of the chest, abdomen and pelvis every 3 cycles (9 weeks). A minimum of three patients will be assessed at each dose level until the maximum tolerated dose has been determined. Please see section 6.1 for details.

DOSE ESCALATION SCHEDULE		
Dose Level	CB-839 (mg) orally twice daily x 21 days	Capecitabine (mg/m  ) orally twice daily for 14/21 days
-1	400	500
1	400	750
2	600	750
3	600	1000
4	800	1000
3A	400	1000

\*3A to be conducted only if dose level 3 is too toxic\*

### 3.2 Study design for phase II component

The phase II portion of the study is a single arm design, assessing the disease control rate of combination therapy with CB-839 and capecitabine chemotherapy in patients with metastatic PIK3CA mutant colorectal cancer who have developed fluoropyrimidine resistance. Patients will receive combination therapy with CB-839 and capecitabine for 21 day cycles and will remain on treatment until either disease progression, development of unacceptable toxicity or discontinuation per patient/physician preference. Patients will receive CB-839 800 mg orally twice daily for 21 days (continuous administration) and capecitabine 1000 mg/m^2 orally twice daily for 14/21 days as was determined during the phase I portion of the study. Patients will undergo blood and tissue sampling at baseline and 10-15 days post-treatment for assessment of glutaminase activity. Tissue specimens will also be assessed for changes in nucleotide levels as well as for a whole exome analysis, an RNA seq analysis and for the generation of organoids. Patients will undergo a CT of the chest, abdomen and pelvis following 3 cycles of therapy (every 9 weeks).

### **3.2 Number of Patients**

A total of 9-24 patients will be enrolled in the phase I portion of this trial and a total of 18-40 patients will be enrolled in the phase II portion of this trial.

### **3.3 Replacement of Patients**

3.3.1 Phase I: If a patient is withdrawn from the study for any reason other than a dose limiting toxicity prior to completing the first 21 days of combination therapy with CB-839 and capecitabine, a replacement patient will be enrolled and will be assigned to the same dose level.

Unless the patient has had their study drug held for an adverse event that may herald a DLT, if a patient does not take at least 75% of the planned doses of each of the two agents (CB-839 and capecitabine), the patient will be replaced because he/she has not taken enough drug to confirm safety at that dose level.

3.3.2 Phase II: If a patient does not take at least 75% of the planned doses of each of the two agents (CB-839 and capecitabine) prior to the first disease assessment (9 weeks), the patient will be replaced because he/she has not taken enough drug to assess efficacy.

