#### 6.4 Definition of Dose-Limiting Toxicity

Patients must receive at least 75% of the planned CB-839 and capecitabine administrations in the

first treatment cycle to be considered evaluable for DLT, unless the patient experiences a DLT or has the study drug held for an AE that may herald a DLT. Patients who discontinue the study prior to receiving the requisite study treatment administrations for reasons that include, but are not limited to, clinical/radiographic progression, voluntary withdrawal, or complications that the Principal Investigator considers secondary to the patient's malignancy will not be considered evaluable for DLT and will be replaced.

A DLT is defined as any AE that cannot be determined to be unrelated to study treatment, occurs within the first treatment cycle (i.e., Cycle 1), and that meets at least one of the non-hematologic or hematologic criteria below:

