## **12.5 Progression Free Survival**

Progression-free survival (PFS) is defined as the duration of time from start of treatment to time of progression or death, whichever occurs first.

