## **14.0 STATISTICAL CONSIDERATIONS**

### **14.1 Study Design/Endpoints**

#### **14.1.1 Definition of Primary Endpoint**

Phase I: Safety, tolerability and recommended phase II dose (RP2D) of combination therapy with CB-839 and capecitabine chemotherapy in patients with no remaining treatment options or patients for whom single agent capecitabine is an acceptable therapy.

Phase II: : Progression free survival (PFS) on combination CB-839 and capecitabine as determined by clinical assessment and RECIST criteria in patients with metastatic PIK3CA mutant colorectal cancer who are refractory to fluoropyrimidine based therapy. Progression free survival is defined as the time from randomization to documented progression or death without progression.

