## **14.2 Analytic Plan for Primary Objectives**

The phase I component of this study is a dose-escalation trial of CB-839 and capecitabine in patients with advanced solid tumors for whom there are no remaining treatment options or for whom capecitabine is an acceptable treatment. It has been designed to define the recommended phase II dose of CB-839 and capecitabine. A traditional 3+3 dose escalation design will be adopted. Nine to twenty-four patients are expected to be enrolled, depending on the number of dose escalations and assuming that a total of 6 patients will be treated at the final recommended phase II dose level. Patients who complete the first 21 day treatment cycle of CB-839 and capecitabine chemotherapy will be included in the analysis. Patients who do not complete the first 21 day treatment cycle or who fail to receive at least 75% of the doses of both CB-839 and capecitabine for reasons unrelated to toxicity will not be included and must be replaced.

In the phase II component of this study, the primary endpoint is progression free survival rate at 6 months with a null hypothesis of 18% vs. a target of 36%. Employing a 2-stage design, and assuming 80% power and a 0.05 significance level, 40 total patients will be required with 18 in the first stage and the probability of early stopping if the null hypothesis is correct (<3/18 patients with stable disease at 6 months) will be 0.589. If at least 3 patients in 18 has stable disease or better at 6 months, an additional 22 patients will be treated (total of 40 patients). If antitumor activity is identified in the PIK3CA mutant population, we will consider amending the phase 2 trial to assess an additional cohort of patients with wild-type PIK3CA. The statistical considerations will follow the same rules as in the original mutant cohort. Response rate will be determined using RECIST criteria.

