## **14.3 Analytic Plan for Secondary Objectives**

All toxicities will be summarized as the percentage of patients experiencing each type and grade of event according to dose level. Patients who receive at least one dose of treatment will be included in the analysis.

In the phase I portion of the study, response rate will be summarized using frequencies and proportions by dose level. Response to treatment will be determined using RECIST criteria.

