#### **14.4 Analytic Plan for Correlative Objectives**

All correlative studies will be performed in biospecimens from the intent to treat population of 18-40 patients from the phase II portion of the study. Pre- and post-treatment tumor samples from the same patients will be used for assessments, except glutaminase activity, which will be performed on post-treatment samples only (tumor samples and platelet samples). All correlative continuous measurements will be summarized using mean +/- SEM, range and median; all categorical measurements will be summarized using frequencies and proportions. Change in these measurements in tumors before and after therapy will be assessed using paired Wilcoxon tests. Unpaired Wilcoxon tests will be used for assessment of glutaminase activity in post-treatment samples only. Assuming a maximum of 40 patients (2-sided test with 0.05 significance level and 80% power), for the paired T-test we can detect normalized differences of 4.5 to 18.2% for standard deviations of the difference between pairs ranging from 0.10 to 0.40. Correlations of plasma trough levels and platelet glutaminase activity will be calculated using Spearman correlation coefficients. Assuming a maximum of 40 patients, 2-sided test with 0.05 significance level, we have >98% power to detect a Spearman correlation coefficient of 0.60 or higher.

Whole exome sequencing and RNA sequencing will be performed on pre and post treatment tissue samples and compared for differences for all patients (n=40 patients maximum). All of these analyses are exploratory, hence no power calculations are shown.

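### Phase II patients are replaced for taking under 75% of planned doses of either drug, and the plan does not say whether they stay in the 18 and 40 counted for the primary decision

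*Combined protocol and SAP*

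**What the plan says.** Section 3.3.2 sets the phase II trigger at 75% of the planned doses of each of the two agents, so a shortfall in either one is enough. The consequence reads: "prior to the first disease assessment (9 weeks), the patient will be replaced because he/she has not taken enough drug to assess efficacy". Planned doses are not defined, and no reason for the shortfall is exempt. The phase I rule in 3.3.1 does exempt drug held for an adverse event that may herald a dose-limiting toxicity.

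The plan says who is counted for most other analyses:

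- **Phase I primary analysis (14.2):** patients short of doses "for reasons unrelated to toxicity will not be included and must be replaced".
- **Dose-limiting toxicity (6.4):** patients who stop before receiving the required doses "will not be considered evaluable for DLT and will be replaced".
- **Toxicity (14.3):** "Patients who receive at least one dose of treatment will be included in the analysis".
- **Objective response (12.1):** measurable disease, at least one cycle and a re-evaluation. Objective progression before the end of cycle 1 also counts as evaluable.
- **Correlative studies (14.4):** these "will be performed in biospecimens from the intent to treat population of 18-40 patients".

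There is no such statement for the phase II primary endpoint. Section 14.2 gives a 6-month progression-free survival (PFS) rate of 18% against 36%, and a stage 1 rule: "If at least 3 patients in 18 has stable disease or better at 6 months, an additional 22 patients will be treated". Section 14.1.1 states: "Progression free survival is defined as the time from randomization to documented progression or death without progression". Section 12.5 states: "Progression-free survival (PFS) is defined as the duration of time from start of treatment to time of progression or death, whichever occurs first". The two differ in start date, but neither sets a dose condition.

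**The concern.** A patient who dies early, or who stops early for toxicity or clinical decline, will often fall below 75% of planned doses. Under 12.5 an early death or progression is a failure at 6 months. If replacement also takes the patient out of the count, entry to the primary set depends on something that happens after treatment starts and is plausibly linked to the outcome. An inactive regimen could then score above its true rate, which would make futility stopping less likely and a false positive more likely.

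If instead replaced patients are counted along with their replacements, the numbers exceed 18 and 40, and the plan gives no boundary for the larger numbers. The trial is single-arm and a few patients can decide it, so the choice should not be left until outcomes are known.

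**Working it through.** **Reproducing the design.** Inputs from 14.2: null 18%, target 36%, 18 patients in stage 1, 40 in total, early-stopping probability 0.589. The final cut-off is not stated. Let X1 ~ Bin(18, p) and X2 ~ Bin(22, p).

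- P(X1 ≤ 3 | 0.18) = 0.589, which matches the plan. The rule as written, fewer than 3, gives P(X1 ≤ 2) = 0.346. I use ≤3.
- P(success) = P(X1 > 3 and X1 + X2 ≥ c). At 18% and 36%: c = 11 gives 0.081 and 0.869, c = 12 gives 0.041 and 0.807, and c = 13 gives 0.019 and 0.717. Only c = 12 meets both 0.05 and 80% power, so I take ≥12/40 as the derived cut-off.

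**Reading 1: replaced patients are dropped and extra patients enrolled until 40 count.** Let f be the share replaced and q their 6-month PFS rate. Neither is in the documents, so both are assumed. With a true overall rate of 18%, the rate among those counted is (0.18 − f·q)/(1 − f). Each cell shows type I error / early-stopping probability.

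| Replaced patients' rate q | f = 5% | f = 10% | f = 20% |
|---|---|---|---|
| 0 (all fail) | 0.058 / 0.547 | 0.082 / 0.501 | 0.160 / 0.398 |
| 9% (half) | 0.049 / 0.568 | 0.059 / 0.545 | 0.088 / 0.490 |
| 18% (equal) | 0.041 / 0.589 | 0.041 / 0.589 | 0.041 / 0.589 |
| 27% (better) | 0.035 / 0.610 | 0.028 / 0.633 | 0.016 / 0.688 |

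Example: f = 10%, q = 0 gives 0.18/0.90 = 0.200. Type I error reaches 0.05 at a counted rate of 0.1851, that is, f = 2.8% if all replaced patients fail, or 5.4% at half the rate. Enrolment needed is 40/(1 − f), about 43, 45 and 50. With stop ≤2, as the text is written, the f = 10% figures are 0.086 (all fail) and 0.063 (half).

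**Reading 2: dropped, but enrolment capped at 40 (section 3.2, Number of Patients).** The counted totals are 40(1 − f) = 38, 36 and 32. With 18 still counted in stage 1, the cut-off left at 12 and all replaced patients failing, type I error is 0.042, 0.041 and 0.040. Early stopping falls as in the first row of the table. If the counted rate is 36%, power is about 0.75, 0.68 and 0.49.

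**Reading 3: counted in addition.** As an example, with 20 in stage 1 and 44 in total, stop ≤3 and a true rate of 18%, type I error is 0.079 with the cut-off left at 12 and about 0.04 with 13.

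**Who falls under the rule.** If planned doses means the full nine weeks, capecitabine is 3 × 14 × 2 = 84 doses and CB-839 is 63 × 2 = 126.

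- *Permanent stop.* Last capecitabine on day 45 gives 62/84 = 73.8%, and on day 46 it gives 64/84 = 76.2%. Last CB-839 on day 47 gives 94/126 = 74.6%. Anyone stopping both drugs for good by about day 45 to 47, depending on the scan date, is replaced. That includes early progressors.
- *Dose holds.* Missing 11 capecitabine days (62/84) or 16 CB-839 days (94/126) also triggers the rule. Sections 7.0, 7.1.2 and 7.2.1 allow holds of that kind without withdrawal, so such a patient may still be on study and progression-free.

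If planned doses end at progression, or if 12.1 governs the count, a compliant patient with documented early progression stays in. Early deaths and undocumented early stops are not rescued by 12.1.

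**The case against.** A reader might infer that the plan excludes these patients and so inflates type I error. The documents do not support that. Section 3.3.2 says replaced, not excluded. The stated reason and the phase I rules suggest dropping; the PFS definitions, which have no dose condition, and the intent-to-treat label in 14.4 (for specimens only) suggest counting.

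Nor is the direction fixed. Long dose holds can put progression-free patients among those replaced, and if replaced patients do better than the rest the test becomes conservative. The inflated figures also need more than the 40 patients that section 3.2 says will be enrolled; under a cap of 40 with the cut-off at 12, type I error stays near 0.04. At 5% replaced with half the rate it is 0.049, still below 0.05. All of this stands.

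A reader might also infer that counting replaced patients voids the two-stage design. It does not, if the decision is taken on the first 18 and 40.

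What the objection does not remove is the gap itself: no section settles which reading applies. Section 12.1 fills it only in part, since it concerns objective response and does not keep a patient who dies or stops without re-evaluation.

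**Conclusion.** The concern holds as an undefined primary denominator, and it should be fixed. Replacement depends on a post-baseline dose test with no exception for death, progression or toxicity, and the plan is silent on whether replaced patients count.

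If they are dropped and extra patients enrolled, type I error across the assumed range of 5 to 20% replaced runs from 0.016 (replaced patients do better) through 0.041 (equal) to 0.160 (20% replaced, all failing, an upper bound). If enrolment is capped at 40, the loss is in patients counted and in futility stopping, not in type I error. If replaced patients are added to the count, the stated numbers are exceeded.

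These figures assume the derived cut-off of 12/40, stopping at ≤3/18, and that the 18% null describes all treated patients, for which 14.2 gives no source. The size and direction of any actual bias cannot be known from the documents.

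**What to change.** In 3.3.2 and 14.2, with 12.1 brought into line:

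- Base the stage 1 and final decisions on the first 18 and 40 eligible patients who take at least one dose, with progression or death before 6 months counted as failure.
- Limit replacement in the primary analysis to patients never dosed or found ineligible on pre-treatment data.
- Define planned doses, and keep the set with at least 75% of doses as a labelled sensitivity analysis.
- State in advance how unknown 6-month status is handled, for example as non-success, with a Kaplan-Meier 6-month PFS estimate as sensitivity analysis.
- Apply the same set once the primary endpoint is reconciled. Sections 2.1.2, 3.2 (phase II design) and 14.5 name disease control rate, 12.0 names response rate, and 14.1.1 and 14.2 name PFS.

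The cost is wording, with no extra patients and no change to treatment. The downside is that the observed rate may be somewhat lower: scheduled CTs continue only on treatment (11.2.2), so some progression-free early stops may have unknown status. Power is 0.807 at a true rate of 36%, 0.771 at 35% and 0.731 at 34%. Recording progression status at the 3-monthly follow-up in 6.7 would reduce the unknowns.
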